10.3 Storage of Study Equipment or Related apparatus

R848 will be stored in labelled storage vials in a -20°C freezer within CUH in PI's laboratory and defrosted on the day of usage. Saline will be stored at room temperature. All other clinical equipment will be stored either in the PI's laboratory or the CRF.

10.4 Compliance with Study Treatment

Participants will be administered R848 or saline via a nebuliser directly by the research team and therefore compliance will be directly assessed.

11. SAFETY REPORTING DEFINITIONS

11.1 *Adverse Event (AE)*

An AE or adverse experience is any untoward medical occurrence in a participant, which does not necessarily have a causal relationship with the intervention. An AE can therefore be any unfavourable and unintended sign (including an abnormal laboratory finding), symptom or disease temporally associated with the study, whether or not considered related to the study.

11.2 *Serious Adverse Event (SAE)*

A serious adverse event or reaction is any untoward medical occurrence that at any dose:

- Results in death,
- Is life-threatening,

NOTE: The term "life-threatening" in the definition of "serious" refers to an event in which the participant was at risk of death at the time of the event; it does not refer to an event which hypothetically might have caused death if it were more severe, including an event which:

- Requires inpatient hospitalisation or prolongation of existing hospitalisation,
- Results in persistent or significant disability/incapacity, or
- Is a congenital anomaly/birth defect.
- Other important medical events*

*Other events that may not result in death, are not life threatening, or do not require hospitalisation, may be considered a serious adverse event when, based upon appropriate medical judgement, the event may jeopardise the patient and may require medical or surgical intervention to prevent one of the outcomes listed above.

Planned admission to hospital for a pre-existing condition will not be considered an SAE.

11.3 *Expected Adverse Events and Serious Adverse Events Exempt from Recording*

Nasal R848 challenge administered at doses between 10 - 100 µg/mL in healthy participants and those with asthma has previously been well tolerated with no reported SAEs (11, 12).

R848 is a synthetic substance that when given to in the respiratory tract is designed to mimic the effects of a viral infection such as influenza. Therefore, expected AEs that participants may experience include transient flu-like symptoms such as:

- Cough
- Runny nose
- Mild headache
- Low grade fever
- Lethargy
- Myalgia

If a high-grade fever occurs that is more sustained or causes symptoms, then volunteers will be offered an antipyretic such as paracetamol.

Participants with asthma will be carefully monitored after R848 dosing. If their FEV1 drops by >20% then they will be administered nebulised salbutamol as a bronchodilator.

Nasal sampling using nasosorption and nasal cytology brush may cause:

- Nasal irritation and runny nose
- Minor epistaxis
- Watering of the eyes
- Sneezing

There are minimal if any side effects anticipated from the induced sputum procedure and salbutamol will be given as a bronchodilator at the same time of administration in healthy and asthma participants, but recognised side effects of the procedure include:

- Cough
- Tight chest

Expected AEs from blood sampling procedures may include:

- Mild discomfort during venepuncture
- Bruising at venepuncture site

11.4 *Suspected Unexpected Serious Adverse Reactions (SUSAR)*

A serious adverse reaction, the nature or severity of which is not consistent with the applicable product information

11.5 *Reporting Procedures for All Adverse Events*

All AEs occurring during the study observed by the investigator or reported by the participant, whether or not attributed to study, will be recorded on the CRF. The following information will be recorded: description, date of onset and end date, severity, assessment of relatedness to study and action taken. Follow-up information should be provided as necessary.

AEs considered related to the study as judged by a medically qualified investigator or the sponsor will be followed until resolution, or the event is considered stable. All related AEs that result in a participant's withdrawal from the study or are present at the end of the study, should be followed up until a satisfactory resolution occurs.

It will be left to the investigator's clinical judgment whether or not an AE is of sufficient severity to require the participant's removal from treatment. A participant may also voluntarily withdraw from treatment due to what he or she perceives as an intolerable AE. If either of these occurs, the participant must undergo an end of study assessment and be given appropriate care under medical supervision until symptoms cease or the condition becomes stable. The relationship of AEs to the study will be assessed by a medically qualified investigator.

11.6 *Reporting Procedures for Serious Adverse Events*

All SAEs, except those expected ones defined in [section 10.3](#) that do not require immediate reporting, must be reported to the Sponsor within one working day of discovery or notification of the event. The Sponsor will perform an initial check of the information and ensure that it is reviewed at the next R&D Management meeting. All SAE information must be recorded on an SAE form and sent to the Sponsor using the appropriate reporting form and the contact details on there. Additional information

received for a case (follow-up or corrections to the original case) needs to be detailed on a new SAE form which must be sent to the Sponsor using the appropriate reporting form and the contact details on there.

The Sponsor will report all SUSARs to the Research Ethics Committee concerned. Fatal or life-threatening SUSARs must be reported within 7 days and all other SUSARs within 15 days. In addition to the expedited reporting above, the PI shall submit once a year throughout the study or on request an Annual Report to the Ethics Committee which lists all SAEs / SUSARs that have occurred during the preceding 12 months.

12. STATISTICS

12.1 *Description of Statistical Methods*

CXCL10 will be measured in sputum and serum 24 hours after each ascending dose of inhaled R848 (n = 4) and compared to inhaled saline (n = 2). CXCL10 levels will be compared between groups using unpaired t-tests.

Spirometry (FEV₁), physiological assessments (temperature, pulse, blood pressure) and leukocyte differential counts from FBC samples measured after challenge will be compared to baseline values using one-way analysis of variance (ANOVA).

12.2 *The Number of Participants*

Nasal R848 is a suitable method of inducing nasal innate immune responses (evidenced by a rise in interferon levels) in healthy individuals and those with asthma (11, 12). Therefore, it is anticipated that inhaled R848 will have a similar effect in inducing lung and peripheral innate immune responses even in a small number of participants.

The number of participants in each dose cohort of the dose finding phase of the study (n = 4 R848, n = 2 saline) is based on AstraZeneca's clinical trial of their inhaled TLR7 agonist (a compound with similar effects) (10), and was a suitable number of participants for assessing innate immune responses as evidenced by a rise in CXCL10 in sputum and serum.

12.3 *The Level of Statistical Significance*

A P-value of < 0.05 will be taken to indicate statistical significance.

12.4 *Procedure for Accounting for Missing, Unused, and Spurious Data.*

Missing clinical data points will be imputed as the mean of values from that volunteer.

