6. OBJECTIVES

6.1 Primary Objectives

- i. To identify an appropriate dose of inhaled R848 which induces innate immune responses in serum and lungs

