7.2 Primary Outcome Measures

- i. Change in CXCL10 in serum or induced sputum 24 hours after single ascending dose inhaled R848

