9.1.3 Blood

Blood will be collected on the following occasions:

- *Screening (31.5 mL)*: For routine safety and eligibility (9 mL), DNA testing (2.5 mL) and blood for isolation of peripheral blood mononuclear cells (PBMCs) (20 mL).
- *Baseline (14 mL)*: At 0 hours for full blood count (FBC) (4 mL), CRP (5 mL) and serum collection (5 mL).
- *Post intervention (52 mL)*: At 15 minutes, 1 hour, 4 hours, 24 hours and 48 hours for serum collection (25 mL); At 4 hours, 24 hours, and 48 hours for full blood count (FBC) (12 mL) and CRP (15 mL) measurement.

Therefore, a total volume of approximately 100 mL blood will be collected from each volunteer throughout the whole trial including the screening and main study period.

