9.1.4 Induced sputum

This will be performed using hypertonic saline at the screening visit and 24 hours after intervention using standardised techniques (16) over a 15-20 minute period to obtain sputum that can be analysed for CXCL10 levels. Salbutamol will be co-administered as a bronchodilator to reduce the chances of bronchoconstriction.

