10.2 Dose Escalation

The following doses of nebulised R848 will be tested using a single dose escalation design: 0.1, 1, 10, 100 µg/mL. Six volunteers will be involved in each dose cohort with only a single dose given to each participant.

Each participant will be administered a dose of R848 or saline in a volume of approximately 1 mL (optimal volume to be confirmed after testing) using a breath-actuated nebuliser.

At the end of each dose cohort, CXCL10 levels in sputum and blood will be assessed and compared between saline and R848. If there are no statistically significant differences

between groups, and the dose is tolerable for volunteers, then the study will proceed to the next dose cohort.

Spirometry will be monitored regularly after inhaled challenge. Bronchodilator drugs will be available on standby for administration if volunteers have symptoms of breathlessness or tight chest associated with a significant drop in FEV₁ ($\geq 20\%$) from baseline.

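### Section 12.1 tests CXCL10 at each dose as 4 R848 against that cohort's own 2 saline; pooling healthy saline participants, on the log scale, would raise power in cohorts 2 to 4 with no extra participants

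*Combined protocol and SAP*

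**What the plan says.** Section 12.1 (Description of Statistical Methods) sets the comparison at each dose, in sputum and in serum: "R848 (n = 4) and compared to inhaled saline (n = 2). CXCL10 levels will be compared between groups using unpaired t-tests". Section 12.3 adds "A P-value of < 0.05 will be taken to indicate statistical significance", without stating one- or two-sided. Section 10.2 (Dose Escalation) makes the comparison at the end of each cohort and uses its result: "CXCL10 levels in sputum and blood will be assessed and compared between saline and R848. If there are no statistically significant differences" are found and the dose is tolerable, the study moves to the next cohort.

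Section 7.2 defines the primary outcome as "Change in CXCL10 in serum or induced sputum 24 hours after single ascending dose inhaled R848". The samples needed for a change are collected. Section 9.1.3 lists baseline blood, "At 0 hours for full blood count (FBC) (4 mL), CRP (5 mL) and serum collection (5 mL", and section 9.1.4 says induced sputum is "performed using hypertonic saline at the screening visit and 24 hours after intervention". Section 12.1 gives neither baseline sample a role in the CXCL10 analysis and mentions no transformation.

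The primary objective in section 6.1 is "To identify an appropriate dose of inhaled R848 which induces innate immune responses in serum and lungs". Section 12.2 takes the cohort size from an earlier inhaled TLR7 agonist trial, where it was judged suitable "for assessing innate immune responses as evidenced by a rise in CXCL10 in sputum and serum". It gives no SD, effect size or power.

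Sections 7.1 and 8.4 repeat the 4:2 split in every cohort. Nothing provides for reusing saline participants from earlier cohorts. The stated n = 2 rules out reading pooling into 12.1.

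**The concern.** This comparison answers the only primary objective, and its result enters the escalation step. Four against two leaves 4 degrees of freedom, so the observed difference must be very large to reach P < 0.05. All healthy cohorts share one comparator, nebulised saline, so the trial will hold more relevant control data than the test uses. It will also hold more information on residual variance, because each cohort is analysed as if the others had not been run.

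Two further gaps affect the same sentence of 12.1. The outcome is a change while the test is on levels. The measurement scale is not stated either, which matters for a t-test on so few values if CXCL10 is right-skewed. What is at stake is how often a moderate response is recognised, and how precisely the response at each dose is reported.

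**Working it through.** **Inputs from the documents.** 4 R848 and 2 saline per cohort (7.1, 8.4, 12.1); four healthy cohorts, up to n = 24 (7.1); threshold 0.05 (12.3). There is no power figure in the plan to reproduce.

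**Assumptions.** Two-sided test, one fluid, normal log values with equal variance, no dropout. The effect d is in within-group SDs of the 24-hour log value, shown from 1 to 4 because the documents give no value.

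**Formula.** The test statistic has noncentrality d / √(1/4 + 1/n_s), where n_s is the number of saline participants used. Power is the noncentral t probability beyond the critical value on the residual df.

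**Planned comparison, taken on the log scale.** n_s = 2, df = 6 − 2 = 4, critical t = 2.776. The smallest observed difference reaching significance is 2.776 × √(1/4 + 1/2) = 2.40 SD. Power is 15%, 42%, 74% and 92% at d = 1, 2, 3 and 4.

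**Pooled healthy saline.** By cohort k there are 6k participants and k + 1 group means, so df = 5k − 1, with n_s = 2k.

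**Own-cohort saline, residual variance pooled over cohorts.** There are 2k means, so df = 6k − 2k = 4k, with n_s = 2.

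| Cohort | Pooled saline: n_s, df | Power at 2 / 3 SD | Own-cohort saline: df | Power at 2 / 3 SD |
|---|---|---|---|---|
| 2 | 4, 9 | 71% / 96% | 8 | 53% / 86% |
| 3 | 6, 14 | 82% / 99% | 12 | 57% / 89% |
| 4 | 8, 19 | 87% / 99.6% | 16 | 58% / 90% |

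If only the two compared groups supply the variance, pooled saline gives 66%, 77% and 84% at 2 SD. A Welch test on pooled saline gives 61%, 73% and 76% (simulation).

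**Scale.** If the levels are log-normal and the t-test is run on the raw values, as 12.1 literally reads, simulated 4 v 2 power is about 20% at 2 log-SD and 35% at 3 for an assumed log SD of 0.5. It is about 8% and 12% for a log SD of 1.

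**Baseline adjustment** (pooled model plus log baseline, one further df spent, simulation, 2 SD):

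| Baseline-to-24 h correlation | Cohort 1 | Cohort 2 | Cohort 3 | Cohort 4 |
|---|---|---|---|---|
| Unadjusted | 42% | 71% | 82% | 87% |
| 0 | 30% | 65% | 79% | 85% |
| 0.3 | 33% | 69% | 82% | 88% |
| 0.5 | 38% | 77% | 89% | 93% |
| 0.7 | 50% | 90% | 97% | 99% |

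**Price of pooling.** Simulated chance rises per inactive dose, counting either fluid, with fluid correlation 0 to 0.8:
- Random cohort shifts of SD 1.0 in the 24-hour values: unadjusted pooling 7–17% in cohorts 2 to 4; present test and own-cohort form 4–5%.
- SD doubled at doses 3 and 4: pooling 9–13%; present test 2–3%; own-cohort form 4–7%; Welch on pooled saline 5–6%.

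**The case against.** The strongest defence is that concurrent controls are a legitimate choice. Cohorts run in sequence, and recruitment, procedures or assay runs can shift between them. A comparison within the cohort is protected from this; pooled saline is not. The simulations bear this out, so the objection stands against making the pooled form primary without safeguards. It does not defend discarding the other cohorts' residual variance, because the own-cohort form keeps concurrent controls and still gains power. That form does assume similar variance across cohorts.

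A second defence is that responses may be large. At 4 SD the log-scale 4 v 2 test already has 92% power. If both fluids respond by 2 SD and either counts, the planned test finds a response in 54–67% of cases. A one-sided test in one fluid would have 60% power at 2 SD. These points stand, and they limit the gain to moderate responses.

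Three stronger readings are tempting, and the documents support none of them:
- *The trial cannot detect a response, or will usually escalate past an active dose.* With no SD or effect size given, and no statement of whether one fluid suffices, this cannot be shown.
- *Using the baseline samples necessarily raises power.* It lowers power at low correlation. The documents give no correlation, and baseline sputum comes from screening, not from the challenge day.
- *Large effects are reliably found by the test as written.* The 74% and 92% at 3 and 4 SD need a log scale that 12.1 does not state.

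**Conclusion.** The point holds as an inexpensive improvement to the analysis. For a 2 SD response in one fluid, power rises from 42% to 71–87% in cohorts 2 to 4 with pooled healthy saline, or to 53–58% with own-cohort saline and pooled variance. At 3 SD it rises from 74% to 96–99.6% or 86–90%.

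The benefit has limits. Cohort 1 and the asthma cohort gain nothing, later healthy cohorts run only if escalation continues, and very large responses are found either way on the log scale. The figures rest on assumed effects in SD units, normal log values and equal variance; the pooled figures also require stable saline values across cohorts.

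The mismatch between a change outcome and a test on levels is on the face of the documents and depends on none of these assumptions. Confidence is moderate, because the size of the gain turns on effects and correlations that the documents do not give.

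**What to change.** In 12.1, for each fluid, analyse log CXCL10 at 24 hours in one model over all healthy cohorts dosed so far. Report the geometric mean ratio of each dose to saline with its 95% confidence interval, in two pre-specified forms:
- (a) own-cohort saline with residual variance pooled over cohorts;
- (b) all healthy saline to date, with a Welch check.

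State in advance which form governs the reported primary result. If it is (b), assay bridging samples should not be the only trigger for reverting to (a). They detect assay drift, but not drift in recruitment or procedures, nor unequal variance. Plot saline values by cohort.

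Align 12.1 with section 7.2 by adjusting for log baseline (0-hour serum, screening sputum). Acknowledge that this adds useful power only at correlations of about 0.5 or more. In cohort 1 it leaves 3 residual df and costs power unless the correlation is high, so state beforehand whether cohort 1 is adjusted.

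Keep the asthma cohort separate, with its own saline participants, and report it as an estimate with a confidence interval.

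The sponsor should reconcile *or* in 7.2 with *and* in 6.1 on whether one fluid or both must respond, and 10.2 with 12.1 on how a CXCL10 result enters the escalation step. No escalation rule is proposed here.

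The cost is wording, some extra analysis, bridging samples in each assay run, and assaying each participant's baseline and 24-hour samples in the same run. No participants are added. The downside is the reliance on stable saline values for (b), and on similar variance across cohorts for both forms.

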7. STUDY DESIGN

7.1 Summary of Trial Design

Nasal administration of R848 has been shown to cause dose-dependent (10 to 100 µg/mL) induction of mucosal innate immune responses (11, 12). The current study will aim to nebulise R848 into the lower airways using a similar dosing regimen and using a nebulisation technique well established using inhaled lipopolysaccharide (LPS) challenge (15). The design of the study is broadly based on a previously published clinical trial of an inhaled TLR7 agonist (10).

Single ascending dose (0.1, 1, 10, 100 µg/mL) nebulisation of R848 will be performed in healthy volunteers (up to n = 24) and subsequently in volunteers with asthma (n = 6).

All volunteers will receive only a single dose and the starting dose cohort for nebulised challenge will be 100-fold lower than the dose administered in the nose to ensure clinical tolerability.

For each dose-cohort (n = 6), participants will be randomised to either R848 (n = 4) or saline (n = 2).

A summary of the study design is outlined in [Appendix A](#).

The study will start with a small “sample only” cohort of six participants without asthma who will be recruited for the collection of nasal brush, sputum, and blood samples to optimise sample processing protocols prior to the main study.

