8. TRIAL PARTICIPANTS

8.1 Overall Description of Trial Participants

The study will start with a small “sample only” cohort of six participants without asthma who will be recruited for the collection of nasal brush, sputum, and blood samples to optimise sample processing protocols prior to the main study.

The interventional part of the study will be performed in participants without asthma (n = 24), and subsequently in participants with asthma (n = 6).

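### CXCL10 is tested in one cohort of six at a time with no analysis across the ordered doses, so a graded response can be missed and the estimate at the first significant dose is selected upward

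*Combined protocol and SAP*

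**What the plan says.** Section 6.1 gives the primary objective: "To identify an appropriate dose of inhaled R848 which induces innate immune responses in serum and lungs". Section 7.2 gives the primary outcome: "Change in CXCL10 in serum or induced sputum 24 hours after single ascending dose inhaled R848".

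Section 7.1 sets four ascending concentrations in healthy volunteers. Each cohort has six people, randomised 4 to R848 and 2 to saline. Section 12.1 then states that "CXCL10 levels will be compared between groups using unpaired t-tests", and describes the groups as the 4 on R848 at each dose and 2 on saline. Section 12.3 sets P < 0.05, without sidedness or any adjustment for repeated testing.

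The same comparison drives escalation. Section 10.2 has CXCL10 compared at the end of each cohort: "If there are no statistically significant differences" and the dose is tolerable, the study moves to the next cohort. That a significant cohort ends escalation is implied, not stated; section 7.1 supports it with "healthy volunteers (up to n = 24) and subsequently in volunteers with asthma (n = 6".

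The plan has no trend test, dose-response model or other CXCL10 analysis using more than one dose. It does not say how the effect at the chosen dose will be reported, or what follows if no cohort is significant. Section 12.2 justifies the cohort size by analogy with an earlier inhaled TLR7 agonist trial and gives no effect size, SD or power.

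**The concern.** The design is an ordered dose series, and section 7.1 cites a dose-dependent nasal response as its basis. The analysis treats the series as up to four unrelated experiments of six people. Two things follow.

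First, a response that rises steadily with dose can leave every cohort short of significance, although the cohorts together show it clearly.

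Second, the dose that stops escalation is the first to pass a demanding threshold, and the same six people supply its effect estimate. Passing requires a large observed difference, so the estimate is biased upward. Section 5.2 presents the model as a platform for testing anti-inflammatory compounds, so the size of the response at the chosen dose may matter beyond this trial.

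**Working it through.** **The plan's own figure.** The only sample-size figure is the total of 36 in the synopsis. It reproduces as a head count: 6 sample-only + 4 cohorts × 6 + 6 with asthma = 36. There is no power figure to reproduce.

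**Threshold for one cohort.** With 4 v 2, df = 4 + 2 − 2 = 4 and t(0.975; 4) = 2.776 (two-sided, pooled variance; both assumed). The standard error factor is √(1/4 + 1/2) = 0.866. The smallest significant difference is 2.776 × 0.866 = 2.40 estimated SDs.

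**Power for one cohort** (exact noncentral t): 15% at a true effect of 1 SD, 27% at 1.5, 42% at 2, 74% at 3 and 92% at 4. Power of 80% needs 3.26 SD.

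**False selection.** For an inert agent and one fluid, 1 − 0.95⁴ = 18.5% of trials find some dose.

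**The escalation sequence, by simulation.** Assumptions: log CXCL10 normal with SD 1; stop at the first two-sided P < 0.05; no stops for tolerability; correlation 0.5 between serum and sputum where either may count. Effects are in SD at doses 1 to 4.

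| True effects | No significant cohort, one fluid | Either fluid | Mean estimate v mean truth at selected dose, one fluid |
|---|---|---|---|
| 0, 0.5, 1, 1.5 | 55% | 34% | 1.82 v 1.03 |
| 0.5, 1, 1.5, 2 | 33–34% | 15% | by dose, below |
| 0, 0.5, 1, 2 | 43% | 23% | 2.08 v 1.41 |
| 0, 0, 1, 2 | 44–45% | 24% | 1.99 v 1.41 |
| 0, 1, 2, 3 | 12% | 3% | 2.61 v 2.12 |
| 0, 0, 1.5, 3 | 17% | 5% | 2.59 v 2.21 |
| 0, 0, 2, 4 | 4% | 0.6% | 3.08 v 2.80 |
| 1, 2, 3, 4 | 1% | 0.1% | 2.93 v 2.46 |

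For 0.5, 1, 1.5, 2 the mean estimates when selected at doses 2, 3 and 4 are about 2.0, 2.3 and 2.6, against truths of 1, 1.5 and 2. Over the rows with means shown, the overstatement runs from 1.82/1.03 = 1.77 (77%) down to 3.08/2.80 = 1.10 (10%).

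**What a trend across cohorts adds.** Let D_j be the R848 minus saline difference in cohort j, with variance 0.75σ². With cohort as a fixed effect and score j = 1 to 4, the slope is ΣjD_j / Σj², where Σj² = 30. Its standard error is σ√(0.75/30) = 0.158σ, and residual df = 24 − 4 − 1 = 19. For effects 0.5, 1, 1.5, 2 the expected slope is (0.5 + 2 + 4.5 + 8)/30 = 0.5, a signal of 0.5/0.158 = 3.16 standard errors on 19 df. The top cohort alone gives 2/0.866 = 2.31 on 4 df.

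In simulated trials where no cohort was significant (one fluid), the trend is significant in about 37% (0, 0, 1, 2), 68% (0.5, 1, 1.5, 2) and 88% (0, 1, 2, 3). For an inert agent its type I error is about 3% in such trials. Over all trials, including those stopped early on a significant cohort, it is about 12%.

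**What free dose-specific estimates add.** With cohort and dose both as factors, and before baseline adjustment, each point estimate is still that cohort's own difference. Only the residual variance is shared. With all four cohorts run, df = 24 − 4 − 4 = 16 and the 95% half-width is 2.120 × 0.866 = 1.84 SDs, against 2.40.

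**The case against.** The strongest objection is that the risk of finding no dose rests on effect sizes the documents do not give. This stands. At 3–4 SD at the top dose the risk is small, and the outcome wording allows either fluid, which cuts it further (for 0.5, 1, 1.5, 2, from about 33% to 15%). The same latitude raises false selection for an inert agent from 18.5% to about 33%.

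A second objection is that a straight-line dose model would be a poor remedy. This also stands. A line through zero gives every dose the same t statistic, so it cannot say which dose works, and it misleads for threshold shapes: with effects 0, 0, 2, 4 its estimate at dose 4 averages 2.81 against a truth of 4.0. Its gain in bias appears mainly when the true response is linear. The trend should therefore be a supportive test only.

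Third, a reader might infer that every planned test is confined to one cohort. The documents do not support that: the secondary ANOVA in section 12.1 is not said to be per cohort. Nor do they say that a trial with no significant cohort would conclude R848 is inactive, or that later studies will be sized on the estimate from this one.

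Finally, accumulating saline across cohorts alone would reduce the problem (no dose found from 43% to 13% for 0, 0.5, 1, 2). That requires stable saline values between cohorts, and it still neither uses the dose ordering nor removes the selection.

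**Conclusion.** The point holds for the primary outcome. Every planned CXCL10 comparison uses 4 v 2 from one cohort, its result steers escalation, and no analysis spans the ordered doses.

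The size of the risk is conditional. With one fluid and a top-dose effect of 2 SD, about 33–45% of trials have no significant cohort. At 3–4 SD it is about 4–12% for effects 0, 1, 2, 3 and 0, 0, 2, 4, and 1–17% over all four shapes tried. A general claim that the trial will often find no dose goes beyond the documents; equally, section 12.2 gives nothing that rules out the unfavourable range.

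The upward selection is firmer. The mean estimate exceeded the truth in every scenario with a real effect where the two were compared, though by less as effects grow. These results assume log-normal CXCL10, a pooled-variance two-sided test and stopping at the first significant cohort. That stopping rule is inferred, and the Appendix A flowchart was not available to check it. This is a cheap improvement worth making, not a flaw that invalidates the design.

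**What to change.** Leave the escalation rule in section 10.2 as it is. Add to section 12.1 one pre-specified final analysis of all healthy participants in the dose cohorts. Do it separately for serum and sputum, on log CXCL10 at 24 hours, adjusted for baseline where a baseline value exists, with cohort as a fixed effect so that only randomised within-cohort contrasts are used.

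- **Trend.** Test a dose score (saline 0, R848 1 to 4) as supportive evidence of whether R848 induces a response. State that its P value is nominal if escalation stopped on a significant cohort.
- **Estimates.** Report the R848:saline ratio with 95% CI at each dose tested, with dose as a factor and residual variance pooled across cohorts, not forced onto a line. State that the estimate at the stopping dose is selected and probably too large. Do not base the dose conclusion on a linear fit.

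The cost is a paragraph in section 12.1 and a modest extra analysis, with no extra participants or samples. Re-assay in one batch is not needed, because cohort effects absorb between-run shifts on the log scale.

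Limits: the trend test assumes a roughly increasing response, recovers less when the response is weak, and does not identify the dose. The 3% error rate is for one fluid. The factor model narrows the intervals but does not remove the selection, which is why the label is needed.
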